6.9 Criteria for Study Discontinuation

Following are criteria for study discontinuation:

- The parent or legal guardian refuses to allow the subject further treatment and/or follow-up evaluations.
- The investigator determines that further participation would be detrimental to the subject's health or well-being.

- The subject fails to comply with the study requirements so as to cause harm to him/herself or seriously interfere with the validity of the study results.

7.0 EXPEDITED ADVERSE EVENT REPORTING

7.1 Adverse Event Reporting to DAIDS

Requirements, definitions and methods for expedited reporting of Adverse Events (AEs) are outlined in Version 2.0 of the DAIDS EAE Manual, which is available on the RSC website at: <http://rsc.tech-res.com/safetyandpharmacovigilance/>.

The DAERS internet-based reporting system must be used for expedited AE reporting to DAIDS. In the event of system outages or technical difficulties, expedited AEs may be submitted via the DAIDS EAE Form. For questions about DAERS, please contact [contact] or from within the DAERS application itself.

Sites where DAERS has not been implemented will submit expedited AEs by documenting the information on the current DAIDS EAE Form. This form is available on the RSC website: <http://rsc.tech-res.com/safetyandpharmacovigilance/>. For questions about EAE reporting, please contact the RSC ([contact]).

7.2 Reporting Requirements for this Study

- The SAE Reporting Category, as defined in Version 2.0 of the DAIDS EAE Manual, will be used for this study.

The study agent for which expedited reporting is required is Etravirine

- In addition to the EAE Reporting Category identified above, other AEs that must be reported in an expedited manner are:
- Erythema multiforme
- Suspected transmission of an infectious agent by study product (as required by Vol. 9A, section 5.9 of the Rules Governing Medicinal Products in the European Union – Guidelines on Pharmacovigilance for Medicinal Products for Human Use. Such reporting is required irrespective of the presence of other seriousness criteria.)

7.3 Grading Severity of Events

The Division of AIDS Table for Grading the Severity of Adult and Pediatric Adverse Events (DAIDS AE Grading Table, Version 1.0, December 2004, Clarification August 2009) is used and is available on the RSC website at <http://rsc.tech-res.com/safetyandpharmacovigilance/>.

To grade to the severity of any abnormal QTc or PR intervals, the DAIDS AE grading table for these events are described in Appendix V.

To grade the severity of any neurologic events, sites should use the grading table in Appendix VI.

7.4 Expedited AE Reporting Period

- The expedited AE reporting period for this study is as per the EAE manual.
- After the protocol-defined AE reporting period, unless otherwise noted, only SUSARs as defined in Version 2.0 of the EAE Manual will be reported to DAIDS if the study staff become aware of the events on a passive basis (from publicly available information).

NOTE: For reporting of all adverse experiences the Investigator will determine the causality and relationship to study drug. However, in regards to subject safety and PK evaluations which will support the selection of a dose for a given cohort, the protocol team will also have input as to the causality and drug relation of specific adverse experiences.

8.0 STATISTICAL CONSIDERATIONS

8.1 General Design Issues

This is a Phase I/II multicenter, open label study with primary objectives of assessing the safety/tolerability and pharmacokinetics of ETR in combination with optimized background regimen (OBR) administered to HIV-infected treatment-experienced children within the age range of ≥ 2 months to < 6 years.

Hypothesis: ETR will be safe, well tolerated, will have pharmacokinetics comparable to adults and will demonstrate antiviral activity when used with an optimized background therapy in HIV-1-infected, treatment experienced infants and children.

The sample will be stratified into the following age groups:

Cohort I	≥ 2 years to < 6 years of age who are treatment experienced*
Cohort II	≥ 1 year to < 2 years of age who are treatment experienced*
Cohort III:	≥ 2 months to < 1 year who are treatment experienced* †

*Treatment experienced children on a failing combination antiretroviral regimen (containing at least 3 ARVs) for at least 8 weeks OR Treatment experienced children on a treatment interruption of at least 4 weeks with a history of virologic failure while on a combination antiretroviral regimen (containing at least 3 ARVs)

†Subjects below 6 months of age will only be enrolled upon availability of initial safety and PK data from subjects between 6 months and 1 year of age.

A minimum of 12 subjects will be enrolled into each cohort of the study. Up to 18 subjects may be enrolled into Cohort 1. The total sample will include at least 36 evaluable subjects who have been treated exclusively at the doses judged to be optimal for their age cohorts.

NOTE: For the Week 24 (or Week 48) analysis, evaluable will be defined as having been treated exclusively on the dose determined to be optimal for a given age cohort and having either completed 24 (or 48) weeks of exposure to the study drug or having been classified as a safety failure, due to a study drug related adverse event occurring during the first 24 (or 48) weeks of treatment.

Accrual to the study will follow an algorithm in which younger children's (Cohort II and Cohort III) exposure to the study medication is contingent upon the older age cohort (Cohort I) having passed the safety criteria. In addition, sufficient pharmacokinetic data will be required to determine the starting dose for the younger cohort (see Section 3.3-3.4 for details).

Initial tests of safety and PK will examine data from the first 6 subjects (mini-cohort) of Cohort I to determine whether Cohort II and Cohort III will be allowed to open for its mini-cohort of 6 subjects. Subjects below 6 months of age will not be enrolled until there are initial safety and PK data from subjects between 6 months and 1 year of age. These tests will proceed as follows:

- The PK data for the first six subjects of the Cohort I will be evaluated on the basis of blood samples taken 14 days \pm 4 days after the start of therapy.
- Safety will be evaluated on the basis of all available data collected through the 28th day on the dose that is being evaluated (see Section 8.51 for the safety guidelines to be used in the dose-finding algorithm).
- For subjects failing to meet PK targets and requiring individual dose adjustments, safety will be evaluated on the basis of data gathered until the time of the visit at which the dose is adjusted. This will insure that, for subjects needing PK determined dose adjustment, adverse events attributed to the starting dose must have occurred while the subjects were still on that dose. However, this also means that for such subjects the safety of the starting dose may be assessed on the basis of less than 28 days of study drug exposure.

The overall safety and PK data of the first 6 subjects on a given cohort will be evaluated with respect to the guidelines specified in Section 8.512 and in Section 9.0 of the protocol. Once these subjects have passed both PK and safety criteria, 6 additional subjects will be accrued to complete each cohort (up to 12 additional subjects may be accrued to Cohort I). The full cohort must also pass the PK and safety criteria (see Section 8.513 and Section 9.0). If the mini or full cohort fails either the safety or the PK guidelines, then the starting dose will be adjusted in the appropriate direction, (upwards for inadequate PK values; downwards for safety failure), if this is feasible. Subjects in a cohort that failed PK or safety but were receiving the same dose as that recommended in the new dosing cohort will be included in PK and safety analysis of the new dose and additional new subjects will be enrolled as appropriate at the new dose in order to have a mini-cohort of 6 subjects treated with the new dose. An initial evaluation of safety and PK will be made on the basis of data from these subjects. The evaluation will proceed as described above. In the event that the mini- or full cohort fails the PK criteria before the cohort completes accrual, then safety will be evaluated on all available subjects to confirm that a dose increase is not contraindicated.

If the P1090 core protocol team judges a given subject's PK data to be unevaluable, the subject will be replaced for dose finding purposes. Note that the subject would be replaced for evaluating safety, as well as PK, criteria, since unevaluable PK data would reflect uncertainty about appropriate exposure to the study medication.

The study accrual is designed to yield at least 36 evaluable subjects for the Week 24 (and 48) safety analyses, which analyses will occur when the last subject of the last cohort has reached week 24 (or Week 48). For these safety analyses, "evaluable" will be defined as having been treated exclusively on the dose determined to be optimal for a given age cohort and having either completed 24 (or 48) weeks of exposure to the study drug or having been classified as a safety failure, due to a study drug related adverse event

occurring during the first 24 (or 48) weeks of treatment. Although the primary safety analyses will focus on the effects of exposure to the optimal dose level for 24 and 48 weeks, secondary analyses will include all safety data collected from first subject exposure to 24 (or 48) weeks and until the end of the study. This will include data representing the final dose for each cohort, as well as data gathered during the dose finding stage which may represent exposure to doses which have failed. This will also include data from subjects whose individual doses have been adjusted, with results broken down by the times at which different dose levels were taken.

8.2 Endpoints and Outcome Measures

8.21 Primary Endpoints:

Toxicity Endpoints:

- Termination from treatment due to a suspected adverse drug reaction (SADR)
- Adverse events of Grade 3 or higher severity
- Death

Pharmacokinetic Endpoint:

- Failure to meet PK targets (specified in Section 9.0)

8.22 Secondary Endpoints:

- Adverse events of Grade 3 or higher severity judged to be at least possibly attributable to the study medications
- Confirmed failure to suppress plasma HIV-1 RNA to ≤ 400 copies
- AND
- Failure to achieve at least a 2 log reduction (from baseline) in HIV-1 RNA at weeks 24 and/or 48 (confirmed in 1 to 4 weeks)
- Treatment discontinued due to toxicity or virologic failure
- Change in optimized background regimen due to virologic failure
- New onset OI or AIDS diagnosis
- Decline in absolute CD4 percent of $> 5\%$ any time after 12 weeks of therapy

8.23 Primary Response Variables:

- Pharmacokinetic parameters - AUC12h

8.24 Secondary Response Variables:

- Plasma HIV-1 RNA (copies/mL)
- CD4 counts and percent
- CD4/CD8 ratio and percent
- Genotypic and phenotypic measures of resistance at virologic failure and at early discontinuation

- Pharmacokinetic parameters - C_{12h} and C_{max}

8.25 Exploratory Response Variables:

- Patient-specific CYP gene profiles.

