analysis. Additional analyses will look at the combined data from subjects whose doses failed and those who have been treated solely at the optimal doses determined for their cohorts and without individual PK determined dose adjustments. Sensitivity analyses will be performed to determine whether the exclusion of subjects whose doses have been adjusted creates a selection bias which impacts upon any results.

Each subject's safety data will be summarized as: the worst grade of adverse event experienced during the first 24 weeks (and 48 weeks) of exposure to the optimal dose of the study treatment and the worst grade of adverse event judged to be at least possibly related to study treatment during this time period. Frequency distributions of these safety outcomes will be presented in the aggregate and broken down by age. Listings of all Grade 3+ events will be provided, broken down by type of toxicity (hepatic, hematologic etc.).

The proportions of subjects experiencing Grade 3+ adverse events will be presented in aggregate and broken down by age cohort, with these proportions bounded by exact 95% confidence intervals. Similar analyses will present the proportions of subjects exhibiting Grade 3+ events which have been judged to be at least possibly related to study medication, again bounded by exact 95% confidence intervals.

8.632 Key Secondary Analyses

8.6321 Viral Load

Virologic outcomes, based on HIV-1 RNA (copies/ml), will be assessed at weeks 8, 12, 24 and 48. The criteria for success are: at least a 0.5 log₁₀ reduction in HIV-1 RNA (copies/ml) at week 8, at least a 1 log₁₀ reduction in HIV-1 RNA (copies/ml) at week 12 and either HIV-1 RNA ≤ 400 copies/ml or at least a 2 log reduction in HIV-1 RNA at weeks 24 and 48.

For regulatory submissions, at each of these time points the primary definition of virologic outcome will be calculated according to a Missing, Switch or Discontinuation = Failure (MSDF) algorithm – as codified by the FDA's snapshot algorithm. Subjects may be classified as virologic failures if they have missing HIV-1 RNA data throughout the window surrounding the time point of interest. (This window and related details will be defined in the analysis plan.) In addition subjects will be classified as virologic failures at any of these time points if they meet any of the following conditions prior to that time point:

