- a) Discontinuation of study treatment due to reasons other than AE or death and viral load was > 400 copies/mL at last available visit.
- b) Change in background therapy not allowed in the protocol.
- c) Change in background ART substitutions permitted per protocol unless the decision to switch is documented as being before or at the first on-treatment visit where HIV-1 RNA is assessed (Week 4).

Subjects who only discontinued a background ARV or who had formula substitutions (substituting single agents for fixed dose combinations and vice versa of the same ARV) in their OBT are not considered as having OBT changes and will not be analyzed as virologic failures. Otherwise, virologic success will be defined as having HIV-1 RNA ≤ 400 copies/mL by the last available HIV-1 RNA assessment while the subject is on-treatment within the visit of interest window. The proportions of subjects meeting the criteria for virologic success at each of these time points will be bounded by exact 95% confidence intervals, and will be presented both in the aggregate and broken down by age cohort.

Table 9 presents exact 95% confidence intervals around various potential rates of virologic success which might be observed in a total sample of 36 subjects or in subsamples of various sizes (N = 12, 24).

Table 9. Percent of Subjects Meeting Criterion for Virologic Success with Exact 95% Confidence Intervals

N	No. of Subjects (%) with Undetectable RNA	95% C.I.
12	1 (8%)	0.2% -- 38%
24	2 (8%)	1% -- 27%
36	4 (11%)	3% -- 26%
12	3 (25%)	5% -- 57%
24	6 (25%)	10% -- 47%
36	9 (25%)	12% -- 42%
12	6 (50%)	21% -- 79%
24	12 (50%)	29% -- 71%
36	18 (50%)	33% -- 67%
12	9 (75%)	43% -- 95%
24	18 (75%)	53% -- 90%
36	27 (75%)	58% -- 88%
12	11 (92%)	62% -- 99.8%
24	22 (92%)	73% -- 99%
36	33 (92%)	78% -- 98%

8.6322 CD4 Response

Change from baseline to weeks 24 and 48 in CD4 count, CD4 percent and CD4/CD8 ratio and percent will be bounded by 95% confidence intervals and presented both in the aggregate and by age cohort. In addition, the proportions of subjects exhibiting an absolute drop of > 5% in CD4 percent from baseline to weeks 12, 24 and 48 will be presented, bounded by 95% confidence intervals. Subjects who meet any of the conditions (a) to (c) of Section 8.6321 or who have absolute drop of > 5% in their CD4% will be considered as treatment failures in these analyses.

8.6323 HIV Drug Resistance

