9. A urine dipstick should be performed at each of the visits indicated. A complete microscopic urine assessment is required only if a urine dipstick is abnormal.
10. Virology assays should be performed at an IMPAACT/VQA approved laboratory. The Abbott platform MUST be used for the HIV-1 RNA assay.
11. Lymphocyte subsets include CD4 and CD8 assays.
12. Subjects should have taken ETR for at least 7 consecutive days prior to the intensive PK, without missing a dose. Intensive PK should be scheduled so that a witnessed dose of ETR is taken approximately 12 hours after the previous dose. PK dosing within a range of 11 to 13 hours after the previous dose is acceptable. The team suggests that an indwelling catheter such as a saline or heparin lock be used for the intensive PK. Once the subject has arrived at the clinic, he/she should be offered a breakfast appropriate for age. Within 30 minutes following breakfast, the PK medications should be administered followed by the PK sampling at the specified time points. If the subject vomits within 15 minutes of taking study drug, the dose should be repeated. Subjects may resume food intake 2 hours after their dose of ETR at the intensive PK visit. One (1) mL of blood will be collected at the following time points: pre-dose, 1, 2, 4, 6, 9 and 12 hours post dosing. To allow for some flexibility, the 9-hour sample can be collected with a window

of 8 to 10 hours post-dose and the 12 hour sample with a window of 11 to 13 hours. If necessary, the 1-hour post-dose sample and/or the 9-hours post-dose sample can be deleted to reduce the amount of total blood drawn from 7 samples over 12 hours to 5 or 6 samples, over 12 hours.

If a subject requires individual dose adjustment for low or high AUCs, they will be asked to return to clinic to have an intensive PK evaluation between Day 7-14 on the new dose.

If a mini or full cohort fails, the failing subjects may have their ETR dose adjusted. In those cases, subjects will be asked to return to clinic to have a truncated intensive PK between Day 7-14 on the new dose with samples collected at the following time points: pre-dose, 2, and between 3-5 hours post dosing.

Note that a repeat EKG is required at the time of a PK visit required for any of the reasons described above.

13. 1.0mL of blood will be collected for each of the population pharmacokinetic samples. NOTE: An absolute minimum of 0.5 mL is necessary for population PK sample.

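### The CD4-decline endpoint covers any time after Week 12, but the dated analysis tabulates only Weeks 12, 24 and 48, and no rule says whether declines at Weeks 16, 32 and 40 count.

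*Protocol*

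**What the plan says.** **Endpoint.** Protocol 8.22 lists, among the secondary endpoints, a decline of more than 5% in absolute CD4 percent "any time after 12 weeks of therapy". SAP section 5 repeats it. Neither gives an upper time limit.

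**Analysis.** Protocol 8.6322 says that the proportions with an absolute drop of more than 5% "in CD4 percent from baseline to weeks 12, 24 and 48 will be presented", with 95% confidence intervals. SAP 6.5 has the same sentence.

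**Failure rule.** The next sentence in both sections adds that subjects who meet any of conditions (a) to (c) of 8.6321, or who have a drop of more than 5% "in their CD4% will be considered as treatment failures in these analyses". It names no visit for the drop. In 8.6321, conditions (a) to (c) make a subject a virologic failure at a time point "if they meet any of the following conditions prior to that time point".

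**Data.** The schedules in Appendices IA, IB and IC have a lymphocyte subset draw at Weeks 4, 8, 12, 16, 24, 32, 40 and 48, and at the early-discontinuation and virologic-failure visits. A footnote to Appendix IA confirms the content: "Lymphocyte subsets include CD4 and CD8 assays". SAP section 7 gives Weeks 16, 32 and 40 their own analysis windows.

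**The concern.** An endpoint defined over a period and an analysis defined at fixed weeks are different quantities. If the analyst follows 8.6322 or SAP 6.5 as dated, the proportion reported does not estimate the endpoint in 8.22. A child whose CD4 percent falls by more than 5 points at Week 16 and recovers by Week 24 meets the endpoint but appears in none of the three tabulated proportions. The mismatch also runs the other way: Week 12 is tabulated, although the endpoint starts after it.

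What is at stake is the meaning of one reported number. The SAP introduction says that the SAP describes the secondary outcome results to be posted on the public registry. Two analysts working from this text could post different figures for the same endpoint.

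**Working it through.** The plan states no rate, sample size or power for this endpoint, so there is no figure of its own to reproduce. The check has two parts.

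**1. Can a CD4 value from Week 16, 32 or 40 enter a tabulated week?** Target days and analysis windows come from SAP section 7. Visit windows come from Appendices IA to IC: ±7 days at Week 12 and ±14 days from Week 16 on.

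| Visit | Target day ± window | On-schedule days | SAP analysis window |
|---|---|---|---|
| Week 12 | 85 ± 7 | 78–92 | Week 12 (71–98) |
| Week 16 | 113 ± 14 | 99–127 | Week 16 (99–140) |
| Week 24 | 169 ± 14 | 155–183 | Week 24 (141–196) |
| Week 32 | 225 ± 14 | 211–239 | Week 32 (197–252) |
| Week 40 | 281 ± 14 | 267–295 | Week 40 (253–308) |
| Week 48 | 337 ± 14 | 323–351 | Week 48 (309–378) |

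Each on-schedule visit falls wholly in its own window, so no on-schedule value from Week 16, 32 or 40 can reach the Week 12, 24 or 48 proportion. The scheduled CD4 visits after Week 12 and through Week 48 are 16, 24, 32, 40 and 48. Two of the five are tabulated and three are not.

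**2. How much could that matter?** The per-visit probability p of a drop of more than 5 points is an assumption. Suppose first that drops are transient and independent between visits. The chance of at least one drop in k visits is then 1 − (1 − p)^k.

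| Assumed p | Any of 5 visits (16, 24, 32, 40, 48) | Week 24 or 48 | Expected children of 36 |
|---|---|---|---|
| 3% | 1 − 0.97^5 = 14.1% | 1 − 0.97^2 = 5.9% | 5.1 vs 2.1 |
| 5% | 1 − 0.95^5 = 22.6% | 1 − 0.95^2 = 9.8% | 8.1 vs 3.5 |
| 10% | 1 − 0.90^5 = 41.0% | 1 − 0.90^2 = 19.0% | 14.7 vs 6.8 |

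The comparison uses Weeks 24 and 48 because Week 12 lies outside the endpoint. If Week 12 is counted as well, the chance of a drop at any of the three tabulated weeks is 1 − 0.97^3 = 8.7%, 1 − 0.95^3 = 14.3% and 1 − 0.90^3 = 27.1%.

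At the other end, suppose every decline persists. One that starts at Week 16 is then seen at Week 24, and one that starts at Week 32 or 40 is seen at Week 48. For children still measured at those weeks the gap is zero.

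**The case against.** A reader might infer that declines at Weeks 16, 32 and 40 are never counted. The documents do not support that. The failure rule in 8.6322 and SAP 6.5 makes a drop of more than 5% a treatment failure without naming a visit, and it sits beside conditions that count events before the time point. It can be read as carrying a Week 16, 32 or 40 drop forward.

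A reader might also infer that a child who declines at an intermediate visit and then changes regimen or stops treatment is lost from the CD4 analysis. That is mostly wrong too, because conditions (a) to (c) are imported into that analysis. Disallowed background changes are failures under (b). Permitted substitutions decided after Week 4 are failures under protocol (c), and under SAP (c) if made at HIV-1 RNA of 400 copies/mL or more. Discontinuation is a failure under SAP (a), apart from one stated exception. Under protocol (a) it is a failure when the reason was not an adverse event or death and the last viral load exceeded 400. What remains is narrow: stopping for an adverse event or while suppressed under the protocol wording, or a permitted switch while suppressed under the SAP wording.

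It is also fair to say that the SAP does list the any-time endpoint, that independence between visits is implausible when every change shares one baseline value, and that an any-visit count treats each unconfirmed reading as a decline.

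All of this limits the size of the point, but the failure rule does not close the gap:

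- Its timing is undefined. Read as any earlier visit, it would also count drops at Weeks 4 and 8, which the endpoint excludes.
- It describes a composite with discontinuation and regimen change, not CD4 decline alone.
- SAP 6.5 points to conditions in a protocol section, while SAP 6.4 lists a different (a) and (c).

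**Conclusion.** The mismatch stands in both documents. The endpoint runs over all time after Week 12. Its dated analysis uses Weeks 12, 24 and 48, and the SAP windows keep on-schedule values from 3 of the 5 later visits out of it. Isolated declines at those visits are outside the tabulated proportions, and whether the failure rule captures them is not defined. Declines that persist to Week 24 or 48 are counted.

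The size is uncertain. At an assumed 5% per visit it is at most about 23% against 10% (14% against 6% at 3%; 41% against 19% at 10%), and it falls towards zero with persistence. These figures rest on assumed rates and on independence, and they ignore any capture by the failure rule.

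This is a descriptive secondary endpoint. No alpha, power or sample size depends on it, so the correction is worth making but minor.

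**What to change.** In protocol 8.6322 and SAP 6.5:

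1. Add the proportion of subjects with an absolute drop of more than 5 percentage points from baseline at any CD4 measurement after Week 12, cumulatively through Week 24 and through Week 48, with exact 95% confidence intervals, in aggregate and by cohort. In SAP windows this is study days 99–196 and 99–378.
2. State that the endpoint is evaluated through Week 48. As written it has no upper limit, and Appendix IE continues CD4 every 24 weeks in long-term follow-up.
3. Keep the Week 12, 24 and 48 proportions as supportive.
4. State which visits count for the drop of more than 5% in the treatment-failure rule.

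The cost is one more table row from data already collected, plus two clarifying sentences. The trade-off is that single unconfirmed readings will count as declines, and the report should say so.
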